9.2. Sample Size Determination

Approximately 24 participants will be randomly assigned to study intervention such that 20 evaluable participants complete the study.

An evaluable participant is one who receives at least one active dose of AMB for whom a pharmacokinetic sample was obtained and provides data on pharmacokinetic parameters.

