9. STATISTICAL CONSIDERATIONS

9.1. Statistical Hypotheses

No formal hypothesis will be tested. An estimation approach will be used to i) estimate the bioavailability of the test formulation relative to the reference formulation, and ii) for each primary pharmacokinetic endpoint, point estimates and corresponding 90% confidence intervals will be constructed for the ratio of the geometric mean of the test formulation to the geometric mean of the reference formulation.

Success for this study is defined quantitatively as the observed AUC and C_{max} geometric mean ratio of the test formulation to reference formulation falling within 0.6 to 2.5. Both AUC and C_{max} will be used, but AUC (average concentration) is most relevant, because AMB is administered chronically.

The lower and upper limits of success are defined accordingly:

- *Lower limit of success (based on efficacy):* PKPD analysis of adult AMB data (reference formulation) did not show a correlation between exposure and efficacy. However, the lowest approved dose (in Japan), which has shown efficacy is 2.5 mg.

Therefore, we have assumed our lower limit to be the 2.5 mg PK exposure. In relation to the therapeutic dose of 5 mg (to be tested in this study), and assuming linearity (observed in the adult studies), a 0.5-fold change in PK exposure (AUC or C_{max}) for the test formulation relative to the reference formulation, is the lower limit for success.

- *Upper limit of success (based on safety):* In the first time in human study (EE-001), doses up to 15 mg were generally well tolerated (higher doses were associated with an increased frequency of AEs, although there were no SAEs). As the dose to be tested in this study is 5 mg, and 15 mg is considered a tolerated dose, a 3-fold increase in PK exposure (AUC or C_{max}) for the test formulation relative to the reference formulation, is the upper limit for success.

Therefore, the PK exposure (AUC and C_{max}) will be considered both safe and efficacious if the observed geometric mean ratio of test formulation to reference formulation falls within 0.5 to 3.

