9.2.1. Sample Size Assumptions

The sample size assumptions are based on previously reported estimates of within subject CV for AUC $(0-\infty)$ and C_{max} for AMB (study GS-US-300-0112, 2008) [[Volibris](#), 2018].

[Table 3](#) summarizes the estimates of within subject CV for the primary endpoints AUC $(0-\infty)$ and C_{max} .

Table 3 Estimates of within subject CV for the primary endpoints AUC $(0-\infty)$ and C_{max}

CVw: within subject CV	AMB
C_{max}	22%
AUC $(0-\infty)$	15%

The largest of the within subject CV estimates is about 22%, which translate to a standard deviation (SD) of 0.217 on the natural log scale. Based on this SD, the half width of the 90% confidence interval will be 12.5% of the point estimate, approximately 24 subjects will be enrolled to provide at least 20 statistically evaluable subjects.

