9.2.2. Sample Size Sensitivity

Assuming the within subject CV differs from 22% and the number of statistically evaluable subjects is lower than 20, then [Table 4](#) shows the precision (the half width of the 90% confidence interval) for a range of evaluable subjects.

Table 4 Sample Size Sensitivity

Evaluable Subjects	CVw	Precision
20	22%	12.5%
20	34%	19.6%
18	22%	13.2%
18	32%	19.6%
16	22%	14.2%
16	30%	19.6%

Assuming a within subject CV for AUC of 15% (see Section 9.2.1), and with a sample size of 20, if the observed mean AUC ratio of test formulation to reference is 0.6, the probability of the true mean ratio being < 0.5 is $< 0.5\%$. Similarly, if the observed mean AUC ratio of test formulation to reference is 2.5-fold, the probability of the true mean ratio being > 3 is $< 0.5\%$. **So, there is at least 99% probability that the observed AUC will not exceed the boundary of (0.5, 3).**

Assuming a within subject CV for C_{max} of 22% (see Section 9.2.1), and with a sample size of 20, the probability of observing a mean C_{max} ratio of test formulation to reference below 0.5 is $< 2\%$ when the true PK ratio is 0.6. Similarly, if the observed C_{max} ratio of test formulation to reference is 2.5-fold, the probability of the true mean ratio being > 3 -fold is $< 2\%$. **So, there is at least 98% probability that the observed C_{max} will not exceed the boundary of (0.5, 3).**

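### Does the loose definition of an evaluable participant undermine the 12.5% precision on which the sample size rests?

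*Protocol*

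**What the plan says.** Section 9.2 sets the target: "Approximately 24 participants will be randomly assigned to study intervention such that 20 evaluable participants complete the study". The next sentence defines the term: "An evaluable participant is one who receives at least one active dose of AMB for whom a pharmacokinetic sample was obtained". As a further condition, that person must contribute PK parameter data. It does not ask for a test and a reference period from the same person.

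Section 9.2.1 builds the precision on within-subject variability: "The largest of the within subject CV estimates is about 22%, which translate to a standard deviation (SD) of 0.217 on the natural log scale". From this it concludes that "the half width of the 90% confidence interval will be 12.5% of the point estimate", and that "approximately 24 subjects will be enrolled to provide at least 20 statistically evaluable subjects". The term statistically evaluable has no definition of its own. Table 4 in section 9.2.2 "shows the precision (the half width of the 90% confidence interval) for a range of evaluable subjects": at a CV of 22% it gives 12.5% for 20, 13.2% for 18 and 14.2% for 16.

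Section 9.1 tests no hypothesis; "point estimates and corresponding 90% confidence intervals will be constructed for the ratio of the geometric mean of the test formulation" to that of the reference. Section 4.4 defines completion as finishing every phase, including follow-up.

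**The concern.** The precision formula counts pairs, whereas the definition counts people with any PK parameter from any one period. In a crossover model with subject effects, a participant seen in only one period contributes nothing to the within-subject contrast of F1 or F2 with R. If 20 evaluable participants were counted by the definition alone, the target could be reported as met with fewer than 20 pairs. The row of Table 4 for 20 would then be read when the row for 16, say, applied. Because the study is sized on the width of an interval and not on power, this touches the whole justification for the number enrolled. Single-period participants are also possible: the liver, QTc, hypotension and haemoglobin criteria in section 7.1 can each end participation after period 1.

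**Working it through.** **Inputs.** Within-subject CV 22% for Cmax and 15% for AUC (section 9.2.1, Table 3); 90% two-sided interval (section 9.1); three treatments in three periods, six sequences in equal ratio (section 6.3.3); 24 randomised for 20 (section 9.2).

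**Reproducing the stated figure.** Log-scale SD: s = √ln(1 + 0.22²) = 0.2174. With n participants giving both treatments, SE = s·√(2/n) and half-width = exp(t₀.₉₅,df · SE) − 1.

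- n = 20: SE = 0.2174 × √(2/20) = 0.0687.
- df = 2n − 4 = 36: exp(1.688 × 0.0687) − 1 = 12.3%.
- df = n − 2 = 18: exp(1.734 × 0.0687) − 1 = 12.7%.

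The stated 12.5% lies between these. The same two choices give 13.1% to 13.5% for 18 (stated 13.2%) and 14.0% to 14.5% for 16 (stated 14.2%). The plan's figures are therefore right for 20, 18 and 16 pairs.

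**What the definition alone would allow.** Model with subject, period and treatment effects, CV 22%, always 20 people with some PK parameter:

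| Complete + one period only | Half-width |
|---|---|
| 20 + 0 | 12.3% |
| 18 + 2 | 13.1% |
| 16 + 4 | 14.0% |
| 14 + 6 | 15.1% |
| 12 + 8 | 16.5% |

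With random subject effects and an assumed between-subject CV of 30%, the last four rows become 13.0%, 13.8%, 14.7% and 15.9%.

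**Can these rows arise under the stated target?** The target is 20 evaluable participants who complete. Completion means all phases (section 4.4). Permanent discontinuation of study intervention takes the participant out of the study (sections 7.1, 7.1.5), and withdrawal ends both (section 7.2). Someone with only one period is thus not among the 20, and every row below the first is excluded.

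**How many losses the rows would need.** With 24 dosed, four dropouts after period 1 still leave 24 − 4 = 20 complete, hence 12.3%. To have 16 + 4 and only 20 evaluable, four others must yield no PK parameter at all: 8 of 24 lost to the comparison. For 12 + 8, 12 of 24 are lost.

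**The residual gap.** Parameters are derived as data permit and missing ones are not imputed (section 9.4.1), so a completer could lack a parameter in one period. Such a person resembles a two-period participant. In the same model, 18 complete + 2 with two periods gives 12.6% to 12.9%, and 16 + 4 gives 12.9% to 13.5%, depending on the comparison. The counts of 2 and 4 are illustrative; the documents give no rate.

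**The assurances in section 9.2.2.** The margin is ln(0.6/0.5) = ln(3/2.5) = 0.182 on the log scale; the tail probability beyond 0.182/SE is shown as normal / t with 2n − 4 df:

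| Pairs | Cmax (stated <2%) | AUC (stated <0.5%) |
|---|---|---|
| 20 | 0.4% / 0.6% | 0.006% / 0.02% |
| 16 | 0.9% / 1.2% | 0.03% / 0.09% |
| 12 | 2.0% / 2.7% | 0.14% / 0.36% |

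The Cmax statement is reached or exceeded only at about 12 to 13 pairs; the AUC statement still holds at 12.

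**The case for a change.** The strongest case for a change is that the completion condition does not fully cure the wording. Section 4.4 defines completion by phases and the follow-up visit, not by usable AUC or Cmax in the paired periods. The condition is not repeated in section 9.2.1 or Table 4, where the precision is stated. If completion already implied paired data, a one-dose definition would have no purpose. And in an estimation study, the count that supports the precision ought to match the formula.

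The point about wording stands: the definition is looser than the calculation, and a careful reader has to combine two sentences to recover the number meant. The point about consequence does not. The gap that completion leaves open is a completer without a usable parameter. Dosing is supervised with a mouth check (section 6.4) and participants stay in the unit to 48 hours (section 2.3.1), so a missing Cmax should be uncommon. AUC(0-∞) may be missing more often, but the loss is of the two-period kind sized above.

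**Conclusion.** The mismatch in wording is real, but it calls for no change. Read with the completion condition beside it, the target of 20 delivers the stated 12.5%, and the larger half-widths of 13.1% to 16.5% describe participants whom that target does not count.

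A tighter definition would also alter nothing that is done. About 24 are randomised in any case. There is no sample size re-estimation (section 9.2.3), no interim analysis (section 9.5) and no replacement rule tied to the count; the reserves in section 5.4 are mentioned only in connection with rescreening. The PK Parameter Population has its own definition (section 9.3). Success is judged on the observed geometric mean ratio, which section 9.1 places within 0.6 to 2.5 (the wider 0.5 to 3 also appears there), and not on interval width. The 90% intervals will show the precision actually achieved, and an analyst will see at once how many pairs lie behind each.

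This rests on reading the two sentences of section 9.2 together, on the within-subject CVs in Table 3, and on losses near the planned 4 of 24. If completers without usable parameters were frequent, the intervals would widen modestly and visibly, to about 13% to 13.5% with four among 20.

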9.2.1. Sample Size Assumptions

The sample size assumptions are based on previously reported estimates of within subject CV for AUC $(0-\infty)$ and C_{max} for AMB (study GS-US-300-0112, 2008) [[Volibris](#), 2018].

[Table 3](#) summarizes the estimates of within subject CV for the primary endpoints AUC $(0-\infty)$ and C_{max} .

Table 3 Estimates of within subject CV for the primary endpoints AUC $(0-\infty)$ and C_{max}

CVw: within subject CV	AMB
C_{max}	22%
AUC $(0-\infty)$	15%

The largest of the within subject CV estimates is about 22%, which translate to a standard deviation (SD) of 0.217 on the natural log scale. Based on this SD, the half width of the 90% confidence interval will be 12.5% of the point estimate, approximately 24 subjects will be enrolled to provide at least 20 statistically evaluable subjects.

9.2.2. Sample Size Sensitivity

Assuming the within subject CV differs from 22% and the number of statistically evaluable subjects is lower than 20, then [Table 4](#) shows the precision (the half width of the 90% confidence interval) for a range of evaluable subjects.

Table 4 Sample Size Sensitivity

Evaluable Subjects	CVw	Precision
20	22%	12.5%
20	34%	19.6%
18	22%	13.2%
18	32%	19.6%
16	22%	14.2%
16	30%	19.6%

Assuming a within subject CV for AUC of 15% (see Section 9.2.1), and with a sample size of 20, if the observed mean AUC ratio of test formulation to reference is 0.6, the probability of the true mean ratio being < 0.5 is $< 0.5\%$. Similarly, if the observed mean AUC ratio of test formulation to reference is 2.5-fold, the probability of the true mean ratio being > 3 is $< 0.5\%$. **So, there is at least 99% probability that the observed AUC will not exceed the boundary of (0.5, 3).**

Assuming a within subject CV for C_{max} of 22% (see Section 9.2.1), and with a sample size of 20, the probability of observing a mean C_{max} ratio of test formulation to reference below 0.5 is $< 2\%$ when the true PK ratio is 0.6. Similarly, if the observed C_{max} ratio of test formulation to reference is 2.5-fold, the probability of the true mean ratio being > 3 -fold is $< 2\%$. **So, there is at least 98% probability that the observed C_{max} will not exceed the boundary of (0.5, 3).**

9.2.3. Sample Size Re-estimation or Adjustment

No sample size re-estimation is planned to be performed.

9.3. Populations for Analyses

Population	Description
Safety	All randomized participants who take at least 1 dose of study intervention. Participants will be analysed according to the intervention they received.
Pharmacokinetic Concentration	The PK Concentration Population will include all participants for whom at least one PK sample was obtained and analysed.
Pharmacokinetic Parameter	For each PK parameter, the PK Parameter Population will include all participants who provide PK parameter data.

9.4. Statistical Analyses

9.4.1. Pharmacokinetic Analyses

Pharmacokinetic analysis will be the responsibility of the Clinical Pharmacokinetics Modelling and Simulation Department, CPKMS, GlaxoSmithKline. Statistical analyses

of the pharmacokinetic parameter data will be the responsibility of Clinical Statistics, GlaxoSmithKline.

Plasma concentration time data for AMB will be analysed by non-compartmental methods with WinNonlin [version 6.3 or above]. Calculations will be based on the actual sampling times recorded during the study although supplementary analysis will be available based on the nominal times. From the plasma concentration-time data, the following pharmacokinetic parameters will be determined, as data permit: maximum observed plasma concentration (C_{max}), time to C_{max} (t_{max}), area under the plasma concentration-time curve [AUC(0-t) and AUC (0- ∞)], and apparent terminal phase half-life ($t_{1/2}$).

The PK parameters, AUC (0- ∞), AUC(0-t), C_{max} , and $t_{1/2}$ will be transformed using natural logarithms. Missing PK parameters will not be imputed. All data from withdrawn subjects will be listed. No adjustment for multiple tests or comparisons is planned.

Pharmacokinetic data will be presented in graphical and/or tabular form and will be summarized descriptively by treatment. Descriptive summary table, graphics, and treatment will also be provided.

Data will be listed and summarized according to GlaxoSmithKline reporting standards, where applicable. Listings will be sorted by subject, period, noting treatment. Summaries will be presented by treatment. Unless stated otherwise, descriptive summaries will include n, mean, standard deviation (SD), coefficient of variation (CV), median, minimum, and maximum for continuous variables, n and percent for categorical variables and geometric mean, 95% confidence interval (CI), and the between-subject CV (CVb) based on geometric mean for the log-transformed PK parameters.

Version 9.3 (or higher) of the SAS system will be used for statistical analysis of the data as well as to generate tables, figures, and listings.

Any deviation(s) from the original analyses planned in the protocol will be reported in the Reporting and Analysis Plan (RAP) and/or in the Clinical Pharmacology Study Report.

All pharmacokinetic data will be stored in the Archives, GlaxoSmithKline Pharmaceuticals R&D.

9.5. Interim Analyses

No interim analyses are planned.

9.6. Safety Analyses

Safety data will be presented in tabular and/or graphical format and summarized descriptively according to GSK's IDSL standards.

10. SUPPORTING DOCUMENTATION AND OPERATIONAL CONSIDERATIONS

10.1. Appendix 1: Regulatory, Ethical, and Study Oversight Considerations

10.1.1. Regulatory and Ethical Considerations

- This study will be conducted in accordance with the protocol and with:
 - Consensus ethical principles derived from international guidelines including the Declaration of Helsinki and Council for International Organizations of Medical Sciences (CIOMS) International Ethical Guidelines
 - Applicable ICH Good Clinical Practice (GCP) Guidelines
 - Applicable laws and regulations
- The protocol, protocol amendments, ICF, Investigator Brochure, and other relevant documents (e.g., advertisements) must be submitted to an IRB/IEC by the investigator and reviewed and approved by the IRB/IEC before the study is initiated.
- Any amendments to the protocol will require IEC/IRB approval before implementation of changes made to the study design, except for changes necessary to eliminate an immediate hazard to study participants.
- The investigator will be responsible for the following:
 - Providing written summaries of the status of the study to the IRB/IEC annually or more frequently in accordance with the requirements, policies, and procedures established by the IRB/EC
 - Notifying the IRB/IEC of SAE or other significant safety findings as required by IRB/IEC procedures
 - Providing oversight of the conduct of the study at the site and adherence to requirements of 21 CFR, ICH guidelines, the IRB/IEC, European regulation 536/2014 for clinical studies (if applicable), and all other applicable local regulations

10.1.2. Financial Disclosure

Investigators and sub-investigators will provide the sponsor with sufficient, accurate financial information as requested to allow the sponsor to submit complete and accurate financial certification or disclosure statements to the appropriate regulatory authorities. Investigators are responsible for providing information on financial interests during the course of the study and for 1 year after completion of the study.

10.1.3. Informed Consent Process

- The investigator or his/her representative will explain the nature of the study to the participant and answer all questions regarding the study.
- Participants must be informed that their participation is voluntary. Participants will be required to sign a statement of informed consent that meets the requirements of 21 CFR 50, local regulations, ICH guidelines, Health Insurance Portability and Accountability Act (HIPAA) requirements, where applicable, and the IRB/IEC or study centre.
- The medical record must include a statement that written informed consent was obtained before the participant was enrolled in the study and the date the written consent was obtained. The authorized person obtaining the informed consent must also sign the ICF.
- Participants must be re-consented to the most current version of the ICF(s) during their participation in the study.
- A copy of the ICF(s) must be provided to the participant.
- Participants who are rescreened are required to sign a new ICF.

10.1.4. Data Protection

- Participants will be assigned a unique identifier by the sponsor. Any participant records or datasets that are transferred to the sponsor will contain the identifier only; participant names or any information which would make the participant identifiable will not be transferred.
- The participant must be informed that his/her personal study-related data will be used by the sponsor in accordance with local data protection law. The level of disclosure must also be explained to the participant.
- The participant must be informed that his/her medical records may be examined by Clinical Quality Assurance auditors or other authorized personnel appointed by the sponsor, by appropriate IRB/IEC members, and by inspectors from regulatory authorities.

10.1.5. Dissemination of Clinical Study Data

- Where required by applicable regulatory requirements, an investigator signatory will be identified for the approval of the clinical study report. The investigator will be provided reasonable access to statistical tables, figures, and relevant reports and will have the opportunity to review the complete study results at a GSK site or other mutually-agreeable location.
- GSK will also provide the investigator with the full summary of the study results. The investigator is encouraged to share the summary results with the study subjects, as appropriate.

- The procedures and timing for public disclosure of the protocol and results summary and for development of a manuscript for publication for this study will be in accordance with GSK Policy.
- GSK intends to make anonymized patient-level data from this trial available to external researchers for scientific analyses or to conduct further research that can help advance medical science or improve patient care. This helps ensure the data provided by trial participants are used to maximum effect in the creation of knowledge and understanding

10.1.6. Data Quality Assurance

- All participant data relating to the study will be recorded on printed or electronic CRF unless transmitted to the sponsor or designee electronically (e.g., laboratory data). The investigator is responsible for verifying that data entries are accurate and correct by physically or electronically signing the CRF.
- The investigator must maintain accurate documentation (source data) that supports the information entered in the CRF.
- The investigator must permit study-related monitoring, audits, IRB/IEC review, and regulatory agency inspections and provide direct access to source data documents.
- Monitoring details describing strategy (e.g., risk-based initiatives in operations and quality such as Risk Management and Mitigation Strategies and Analytical Risk-Based Monitoring), methods, responsibilities and requirements, including handling of noncompliance issues and monitoring techniques (central, remote, or on-site monitoring) are provided in the Monitoring Plan.
- The sponsor or designee is responsible for the data management of this study including quality checking of the data.
- The sponsor assumes accountability for actions delegated to other individuals (e.g., Contract Research Organizations).
- Study monitors will perform ongoing source data verification to confirm that data entered into the CRF by authorized site personnel are accurate, complete, and verifiable from source documents; that the safety and rights of participants are being protected; and that the study is being conducted in accordance with the currently approved protocol and any other study agreements, ICH GCP, and all applicable regulatory requirements.
- Records and documents, including signed ICF, pertaining to the conduct of this study must be retained by the investigator for 25 years from the issue of the final Clinical Study Report (CSR)/ equivalent summary unless local regulations or institutional policies require a longer retention period. No records may be destroyed during the retention period without the written approval of the sponsor. No records may be transferred to another location or party without written notification to the sponsor.

